16.3 Analysis on Subgroups

Analysis on subgroups as defined in Section 10 will be performed for the primary and key secondary efficacy endpoints. In addition, Fisher's exact test will be performed to assess the association between each subgroup and ORR. Furthermore, to compare PFS time and OS time within each subgroup, the hazard ratio and its 95% CI of each subgroup will be calculated using Cox proportional hazards model.

A forest plot will be created to graphically present ORR and its 95% CIs for the FAS and all the subgroups.

CCI [REDACTED]. In case of low number of subjects within a category (< 11 subjects, which is about 10% of the study population), subgroups will be pooled.

16.4 Other Endpoint Analyses

Analysis sets: FAS

16.4.1 Time to Response per RECIST 1.1

Time to response (TTR) is defined, for subjects with an objective response, as the time from the start of first study treatment to the first documentation of objective response (CR or PR) according to RECIST 1.1, as determined by an IERC which is subsequently confirmed.

$TTR \text{ (in weeks)} = (\text{date of first objective response} - \text{date of first dose of study treatment} + 1) / 7$

TTR will be summarized using simple descriptive statistics (mean, SD, median, min, max, Q1, Q3).

CCI [REDACTED]

CCI

CCI

CCI

CCI

CCI

CCI

16.5 Pharmacokinetic Data

Analysis sets: Safety analysis set

The PK analysis set will consist of all subjects who receive at least one dose of Avelumab, and provide at least one measurable post-dose concentration.

16.5.1 Descriptive PK Analysis

Avelumab concentrations in serum will be listed in tables and descriptively summarized by treatment, day and nominal time using the number of non-missing observations (N), number of missing observations (NMiss) arithmetic mean (Mean), standard deviation (SD), coefficient of variation (CV%), standard error of the mean (SEM), minimum (Min), median (Median) and maximum (Max). The pre-dose samples will be considered as if they had been taken simultaneously with the administration. Additional tables listing trough concentrations (Cmin) per cohort/day/administration will also be provided, and summarized descriptively using the aforementioned statistics.

For the calculation of descriptive statistics, values as presented in the data listings will be used. Concentrations will be set to missing in summary tables if the value is reported as N.R. (No result). PK concentrations below the lower limit of quantification (<LLOQ) are taken as zero for descriptive statistics. Minimum and maximum will be presented to the same decimal precision as collected. Mean, median and GeoMean will be presented to one decimal place more than the precision of the data collected. SD and SEM will be presented to two decimal places more than the precision of the data collected. The coefficient of variation (CV%), GeoCV and the 95% CI will be reported to 1 decimal place.

Drug concentration in serum for ADA ever-positive subjects versus ADA never-positive subjects will be descriptively summarized to evaluate the potential effect of ADA on pharmacokinetics.

16.5.2 Population Pharmacokinetic Analysis

Sparse sampled PK profiles from study EMR100070-003 Part B will be analyzed jointly with data CCI and other emergent studies with evaluable PK data by non-linear mixed effect approach, in order to describe the PK concentration time profile followed by multiple dose infusion of avelumab, to identify covariates explaining (part of) the between patient PK variability and to estimate the residual PK inter-individual variability. More details will be given in a separate Data Analysis Plan for Population Pharmacokinetic Analysis. The results will be reported separately.

16.5.3 Relation of Pharmacokinetics to Efficacy

The exposure-response analysis will include FAS subjects for primary analysis from Part B of the study.

Each subject will be classified as responder or non-responder based on BOR according to RECIST 1.1 (responder: CR and PR; non-responder: stable disease [SD], progressive disease [PD], non-evaluable [NE]). The results will be reported separately.

CCI

The influence of the exposure parameter CCI on response will be explored graphically by depicting response (no/yes) versus exposure and applying a spline function to the data.

The relationship between exposure and response will then assessed using logistic regression.

CCI

CCI [Redacted]

Based on this model, the probability of being responder will be depicted versus CCI [Redacted]. A 95% confidence interval will be added to the graph.

In a next step, covariates will be inserted in the logistic regression model.

CCI [Redacted]

Significance of covariates CCI [Redacted] will be assessed using the Wald statistic ($\alpha=0.05$). All covariates will be inserted in the logistic regression model simultaneously and insignificant covariates will be eliminated one by one (starting with the most insignificant covariate) until all remaining covariates are significant.

The odds ratios with 95% confidence intervals for the significant covariates will be calculated and graphically presented in a Forest plot.

Covariates to be tested include, but are not limited to, the following:

CCI [Redacted]

CCI

All exposure-response calculations will be done using the software program R or other software.

CCI

17 Safety Evaluation

Analysis sets: Safety analysis set

17.1 Adverse Events

Treatment emergent adverse events (TEAEs) are those events with onset dates occurring during the on-treatment period or if the worsening of an event is during the on-treatment period.

All analyses described in Section 17.1 will be based on TEAEs (started during the on-treatment period) if not otherwise specified. The AE listings will include all AEs (whether treatment emergent or not). A separate listing including AEs started after the on-treatment period will also be provided.

- **Related Adverse Events:** adverse events with relationship to study treatment (as recorded on the AE eCRF page, Relationship with study treatment = Related) reported by the investigator and those of unknown relationship (i.e. no answer to the question “Relationship with study treatment”).
- **Serious Adverse Events (SAE):** serious adverse events (as recorded on the AE eCRF page, Serious Adverse Event = Yes).
- **Adverse Events Leading to Treatment Discontinuation:** adverse events leading to permanent discontinuation of study treatment (as recorded on the AE eCRF page, Action taken with study treatment = Drug withdrawn).
- **Adverse Events Leading to Death:** adverse event leading to death (as recorded on the AE eCRF page, Outcome = Fatal, as well as AEs of Grade 5).

- **Immune Related Adverse Events (irAE):** immune related adverse events according to case definition classified by medical review as specified in Appendix II.
- **Infusion Related Reactions (IRR):** IRRs as specified in Appendix II.

Unless otherwise stated adverse events will be displayed in terms of frequency tables: PT and primary System Organ Class (SOC) by decreasing frequency. If an adverse event is reported for a given subject more than once during treatment, the worst severity and the worst relationship to study treatment will be tabulated. Each subject will be counted only once within each PT or SOC and recording period. If a subject experiences more than one AE within a PT or SOC for the same recording period, only the AE with the strongest relationship or the worst severity, as appropriate, will be included in the summaries of relationship and severity.

Changes in toxicity grade, seriousness or outcome of AEs are recorded as separate entries in the eCRF with associated end and start dates (start date equals end date of previous entry). Such entries reporting the same event in such immediately consecutive periods will be considered as one event in the analysis in case of an improvement in toxicity grade. These events will be kept as separate records in the database in order to maintain the full detailed history of the events. The start date of the initial record in the sequence is taken as start date of the entire event. Duration of the AE and the TEAE flag will be adjusted accordingly in the analysis.

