7.4.1.3 Definition of the Adverse Event Reporting Period

The AE reporting period for safety surveillance begins when the subject is included into the trial (date of first signature of informed consent) and continues through the trial's post-treatment safety follow-up period, defined as 10 weeks (Part A) / 90 days (Part B) after the last study drug administration.

Any SAE assessed as related to avelumab must be reported whenever it occurs, irrespective of the time elapsed since the last administration.

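### Part B joins split AE entries only when the grade improves, so a pre-dose AE that stays at the same grade can be flagged as treatment-emergent

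*SAP*

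**What the plan says.** SAP Part B, Section 17.1, describes how AE data arrive: "Changes in toxicity grade, seriousness or outcome of AEs are recorded as separate entries in the eCRF with associated end and start dates". The dates are contiguous, because the "start date equals end date of previous entry". Three kinds of change can therefore split one event: grade, seriousness and outcome.

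The same paragraph gives one condition for putting the entries back together. They "will be considered as one event in the analysis in case of an improvement in toxicity grade". For a joined sequence, "The start date of the initial record in the sequence is taken as start date of the entire event", and "Duration of the AE and the TEAE flag will be adjusted accordingly in the analysis".

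Section 17.1 defines TEAEs: they "are those events with onset dates occurring during the on-treatment period or if the worsening of an event is during the on-treatment period". Section 11 starts the on-treatment period at the first dose.

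AEs can exist before that. Protocol Section 7.4.1.3 collects them from informed consent, and Protocol Section 7.1.1 allows up to 18 days of screening before treatment.

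**The concern.** There are three triggers for splitting and one condition for joining. An entry opened by a change of outcome or seriousness, with the grade unchanged, has not improved in grade, so the joining rule does not reach it. Neither does the correction of start date and TEAE flag. Its own start date is the date of the change, which may fall on treatment even though the event began before any avelumab was given.

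The resulting order makes no sense for safety reporting: a pre-dose event that improves is kept out of the TEAE tables, while one that stays the same is let in. TEAE incidence by preferred term is a main safety output of Part B, and its counts should not depend on how entries are divided in the eCRF. The irAE listing in Section 17.2.3 also reports time from first and from most recent dose, and duration. For an entry left unjoined, these run from or to the split and not from true onset to true end.

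**Working it through.** The plan gives no figure to reproduce, and the rule itself involves no arithmetic. The check applies the written rules to an AE that starts after consent and before the first dose, is still ongoing at first dose, and has one change on treatment.

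| On-treatment change | Joined under Section 17.1? | Start date used | TEAE? | Correct? |
|---|---|---|---|---|
| (a) Grade improves | Yes | First entry, pre-dose | No | Yes |
| (b) Grade worsens | No | Date of change | Yes | Yes, by the worsening clause |
| (c) Same grade, outcome changes | No | Date of change | Yes | No: neither onset nor worsening |
| (d) Same grade, serious to non-serious | No | Date of change | Yes | No: if anything, better |
| (e) Same grade, non-serious to serious | No | Date of change | Yes | Defensible as worsening, but not stated |

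An illustration of (a) against (c): Grade 2 fatigue starts on Day -6. If it drops to Grade 1 on Day 9, the entries are joined, onset is Day -6, and it is not a TEAE. If on Day 9 only the recorded outcome changes, with the grade still 2, the second entry starts on Day 9 and is flagged. This assumes an eCRF outcome option short of recovery that opens a new entry; the documents do not list the options.

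Rows (c) and (d) are the errors. Row (e) needs a statement of intent. A change to a fatal outcome would normally bring Grade 5 and so falls under (b).

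For the irAE listing the event need not start before dosing. Any irAE split at an unchanged grade leaves a first entry that ends at the split and a later entry whose onset is the split date.

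The Part A SAP contains no joining rule, so the point concerns Part B only.

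**The case against.** The best reply is that Section 17.1 defines TEAEs by event, and calls the split records entries reporting the same event. On that reading a same-grade outcome change is neither the onset nor the worsening of the event, so it is not a TEAE, and the SAP nowhere says that it is. A programmer could read it so. But the paragraph states that the TEAE flag is adjusted for joined entries, which implies that it is otherwise set entry by entry. At best the case is undefined; followed literally, it comes out wrong.

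The reply is right that the affected group is narrow. Conditions present at the initial visit that do not worsen are not AEs, and laboratory or other investigational abnormalities below Grade 3 are generally not reported as AEs (Protocol Section 7.4.1.1). The AE must start within roughly 18 days, still be ongoing at first dose, and then change without a change of grade. Each subject counts once per preferred term, so a subject with a genuine on-treatment event of that term adds nothing. The eCRF entry rules sit in completion guidelines that are not among the documents.

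Three stronger readings are tempting and are not supported:

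- That every same-grade split of a pre-dose AE is a miscount. Row (e) can fairly be counted as a worsening.
- That the serious and related subsets are materially inflated. A change from serious to non-serious leaves a non-serious later entry, so only an outcome change in a pre-dose SAE that is still serious remains. An event that began before any avelumab is unlikely to be recorded as related.
- That the 7-day criterion in Table 13 of Appendix II is corrupted. Medical reviewers apply it to whether the AE resolves spontaneously. Closing an entry because outcome or seriousness changed is not resolution, and the database keeps the full history.

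**Conclusion.** The concern holds as a defect of a stated rule. As written, Section 17.1 can flag a pre-dose AE as treatment-emergent without onset or worsening on treatment, in cases (c) and (d), and it cuts onset and duration in the irAE listing at same-grade splits. This rests on the TEAE flag being set from each unjoined entry's own start date.

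The documents give no rate of such splits, so the number of subjects cannot be derived. A reader might try assumptions: if 30% of 112 subjects had an AE between consent and first dose, and 10% to 30% of those had such a split, then 112 × 0.30 × 0.10 = 3.4 and 112 × 0.30 × 0.30 = 10.1, or about 3 to 10 subjects. Nothing in the documents anchors either percentage, and the calculation does not require the AE to be ongoing at first dose, so it should not be quoted as an estimate. The effect on overall TEAE incidence is probably small.

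A single term near a cut-off is more sensitive. In the table of non-serious TEAEs at 5% or more, with 112 subjects, 5/112 = 4.5% is below the line and 6/112 = 5.4% is above it, so one falsely flagged subject could bring a term in. No efficacy endpoint is affected, and the full AE listing still shows the entries.

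**What to change.** In SAP Part B, Section 17.1, replace the joining condition: directly consecutive entries of the same event form one event unless the toxicity grade increases. The joined event takes the start of the first entry, the end of the last entry, the worst seriousness and the final outcome. Then add one sentence: a same-grade change from non-serious to serious during the on-treatment period counts as a worsening, and so makes the event a TEAE under the existing definition. A grade increase continues to open a new, worsened event.

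The cost is one clause and one sentence in the SAP and a small change to the AE derivation program. No data collection changes, and the separate eCRF records stay in the database.

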17.1.1 All Adverse Events

Adverse events will be summarized by worst severity (according to NCI-CTCAE version 4.0) per subject, using the latest version of MedDRA preferred term (PT) as event category and MedDRA primary system organ class (SOC) body term as Body System category.

In case a subject had events with missing and non-missing grades, the maximum of the non-missing grades will be displayed. No imputation of missing grades will be performed.

The following tables will be created:

- The overall summary of AEs table will include the frequency (number and percentage) of subjects with each of the following summaries:
 - TEAEs
 - TEAEs, grade ≥ 3
 - Related TEAEs
 - Related TEAEs, grade ≥ 3
 - TEAEs leading to permanent treatment discontinuation
 - Related TEAEs leading to permanent treatment discontinuation
 - Serious TEAEs
 - Related serious TEAEs
 - TEAEs leading to death

- Related TEAEs leading to death
- Treatment emergent irAEs
- Related treatment emergent irAEs
- Treatment emergent IRRs
- Related treatment emergent IRRs
- TEAEs by SOC and PT and worst grade
- Related TEAEs by SOC and PT and worst grade
- TEAEs leading to death by SOC and PT
- Related TEAEs leading to death by SOC and PT
- TEAEs by SOC and PT: displaying in separate columns the All TEAEs / Related TEAEs / Grade ≥ 3 TEAEs / Related Grade ≥ 3 TEAEs
- TEAEs excluding SAEs, with frequency $\geq 5\%$ by SOC and PT

A listing of AEs including all relevant information will be provided. In addition, a listing of non-TEAEs will also be provided.

17.1.2 Adverse Events Leading to Treatment Discontinuation

The following overall frequency tables will be prepared for the adverse event actions that lead to treatment discontinuation:

- AEs leading to permanent treatment discontinuation by SOC and PT
- Related AEs leading to permanent treatment discontinuation by SOC and PT

The listing of AEs leading to permanent treatment discontinuation will also be provided with the relevant information.

17.2 Deaths, Other Serious Adverse Events, and Other Significant Adverse Events

17.2.1 Deaths

All deaths, deaths within 30 days after last dose of study drug, death within 60 days after first dose as well as the primary reason for death, will be tabulated based on information from the “Report of Subject Death” and “Survival Follow-Up” eCRFs.

- Number of Deaths
- Number of Deaths within 30 days after last dose of avelumab
- Number of Deaths within 60 days after first dose of avelumab

- Primary Reason of Death
 - Disease progression
 - Adverse event related to study treatment
 - Adverse event not related to study treatment
 - Other
 - Unknown

In addition, date and cause of death will be provided in individual subject data listing together with selected dosing information (date of first / last administration, number of infusions received overall) and will include the following information:

- AEs with fatal outcome (list preferred terms of AEs with outcome=Fatal, as well as AEs of Grade 5)
- flag for death within 30 days of last study treatment
- flag for death within 60 days of first study treatment

17.2.2 Serious Adverse Events

The following overall frequency tables will be prepared for serious adverse events (SAEs):

- Incidence of SAEs by SOC and PT
- Incidence of related SAEs by SOC and PT

The listings of SAEs will also be provided with the relevant information.

17.2.3 Other Significant Adverse Events

The following tables will be created for treatment emergent irAEs:

- The overall summary of irAEs table will include the following categories:
 - All irAEs
 - irAEs leading to death
 - Related irAEs leading to death
 - irAEs
 - irAEs, Grade ≥ 3
 - Related irAEs
 - Related irAEs, Grade ≥ 3
 - irAEs leading to permanent treatment discontinuation
 - Related irAEs leading to permanent treatment discontinuation

- irAEs by worst grade
- Related irAEs by worst grade
- irAEs leading to death, by subcategory and PT
- Related irAEs leading to death, by subcategory and PT
- irAEs by subcategory and PT
- irAEs, grade ≥ 3 , by subcategory and PT
- Related irAEs by subcategory and PT
- Related irAEs, grade ≥ 3 , by subcategory and PT
- irAEs leading to permanent treatment discontinuation by subcategory and PT
- Related irAEs leading to permanent treatment discontinuation by subcategory and PT
- irAEs by subcategory and PT and worst grade
- Related irAEs by subcategory and PT and worst grade

The listing of irAEs will also be provided with the relevant information. The following information will be provided for each irAE:

- The time from first study treatment to start of AE
- The time from most recent study treatment until start of AE
- The duration of the AE

In addition, a listing of irAEs with onset after the on-treatment period will also be provided.

The frequency (number and percentage) of subjects with each of the following will be presented for treatment emergent IRRs:

- IRRs leading to death, by PT
- Related IRRs leading to death, by PT
- IRRs, by PT
- IRRs, Grade ≥ 3 , by PT
- Related IRRs, by PT
- Related IRRs, Grade ≥ 3 , by PT
- IRRs leading to permanent treatment discontinuation, by PT
- Related IRRs leading to permanent treatment discontinuation, by PT
- Serious IRRs, by PT
- Related serious IRRs, by PT
- Time related to first onset of an IRR (infusion 1, infusion 2, infusion 3, infusion 4 or later)

The listing of all IRRs will also be provided with the relevant information with a flag for IRRs with onset outside of the on-treatment period.

CCI

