7.1.5 Post Treatment Follow-up

Subjects with an ADR ongoing at the End-of Treatment visit must be followed up until the ADR resolves, becomes stable, or is considered not clinically significant by the Investigator. In addition, subjects will be followed for any AE suspected to be related to trial treatment, especially for the occurrence of new autoimmune events up to 3 months after the last dose of avelumab.

For subjects who discontinue treatment prior to Week 13, off-treatment interviews (optional for both Part A and Part B) will be scheduled for 13 weeks and 6 months from the start of treatment to collect subjects' current experience with their disease, the study drug, and their experience within the trial. In case of discontinuation later than Week 13 but prior to 6 months of treatment, an off-treatment interview (optional for both Part A and Part B) will be scheduled for 6 months from the start of treatment.

For Part A, subjects without PD at the End-of-Treatment visit will be followed up for disease progression until PD (CT / MRI scans every 6 weeks until Week 55 [12 months] after the first study drug administration, then every 12 weeks using the same procedures and review as while on treatment; for trial sites in Germany, only MRI is to be used). CCI [REDACTED]

For Part B, subjects without PD at the End-of-Treatment visit will be followed for disease progression until PD (CT / MRI scans every 6 weeks until Week 55 [12 months] after the first study drug administration, then every 12 weeks).

After the End-of-Treatment visit, subjects will be followed quarterly for survival (including assessment of any further tumor therapy). The survival follow-up will continue for up to 5 years after the last subject receives the last dose of avelumab or last subject dies, whichever occurs earlier (see Section 5.7 for details of the end of study).

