If a scheduled pre-dose measurement actually occurred post-dose, then the corresponding measurement will be treated and analyzed similar to an unscheduled post-dose measurement.

Baseline for HR and QTc assessments will be derived from the visit where both HR and QT are not missing.

Definition of study day/treatment day:

Treatment day is defined relative to the date of first study drug administration.

Treatment day 1 is defined as date of first study drug administration, the day before is defined as treatment day - 1 (no treatment day 0 is defined).

Definition of on-treatment period:

On-treatment period is defined as the time from the first dose of study treatment through minimum (30 days + last dose of study treatment, start day of new anti-cancer drug therapy – 1 day).

The date of new anti-cancer drug therapy after start date is derived as outlined in [Section 14.2](#).

Standard derivations and reporting conventions:

The following conversion factors will be used to convert days into weeks, months or years:

1 week = 7 days, 1 month = 30.4375 days, 1 year = 365.25 days.

Demographics and physical measurements:

- Age [years]:
 - (date of given informed consent - date of birth + 1) / 365.25
 - In case of missing day, day only: Age [years]: (year/month of given informed consent - year/month of birth)
 - In case only year of birth is given: Age [years]: (year of given informed consent - year of birth)

The integer part of the calculated age will be used for reporting purposes.

- BMI (kg/m²) = weight (kg)/[height (m)]².
- BSA (m²) = ([height (cm) × weight (kg)] / 3600)^{0.5}

For reporting conventions, mean and median should generally be displayed to one more decimal place than the raw data and standard deviation should be displayed to two more decimal places than the raw data. Percentages will be reported to one decimal place. The rounding will be performed to closest integer/first decimal using the common mid-point between the two consecutive values. E.g. 5.1 to 5.4 will be rounded to an integer of 5, and 5.5 to 5.9 will be rounded to an integer of 6.

Unscheduled visits:

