Appendix II Description of criteria for Adverse Events of Special Interest

A two-level approach is pursued to analyze potential immune-related adverse events (AEs):

1. A MedDRA Preferred Term (PT) query is used for each event category (i.e., immune-mediated rash, colitis, pneumonitis, hepatitis, nephritis and renal dysfunction, endocrinopathies and other immune-mediated adverse reactions).
2. AEs identified by the MedDRA PT queries will then be medically reviewed using pre-defined case definitions for immune-mediated adverse reactions.

Level 1:

To identify potentially immune-mediated AEs, MedDRA PT queries will be used to search for AEs of interest in the clinical database. The relevant event categories and corresponding MedDRA PT queries are documented in a version-controlled repository maintained by the Sponsor and finalized for analysis of the current study data prior to DB lock.

The respective MedDRA PT queries will be used to identify AEs reported in the current study that are potentially immune-mediated events.

Level 2:

In a second level (medical review), the potential immune-mediated AEs identified from the search performed at Level 1, will be reviewed by qualified medical personnel to determine whether the AE meets the criteria (case definition) for an immune-mediated adverse reaction based on the following algorithm:

Table 13 Algorithm for immune-related adverse reactions

| Criteria | Description |
|---|--|
| Onset | AE onset after 1st avelumab administration until up to 90 days after last dose |
| Duration | AE does not spontaneously resolve (i.e., without corticosteroids/ immunosuppressant treatment) within 7 days after onset |
| Immunosuppressive therapy | AE treated with corticosteroid or other immunosuppressant therapy. For endocrinopathies only: AE required hormone replacement* and /or (corticosteroid or other immunosuppressive therapy) |
| Etiology | No other clear etiology or Histopathology/biopsy consistent with immune-mediated event |
| All criteria listed in the left column need to be fulfilled for an event to meet the case definition of immune-mediated reaction. | |
| *Hormone replacement will be evaluated for specific endocrinopathy disorders only as follows: 
 • Thyroid disorders (HLT): Thyroid therapy (ATC codes (H03A, H03B)) • Diabetes mellitus (including hyperglycemia): Insulin (ATC code A10A) | |

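### Part B: the irAE case definition admits onset up to 90 days after last dose, but every irAE frequency table stops at 30 days or earlier, so the incidence under that definition is not estimated

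*SAP*

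**What the plan says.** The Part B SAP, Section 17.1, takes irAEs to be "immune related adverse events according to case definition classified by medical review as specified in Appendix II". In Appendix II, the onset criterion of Table 13 is "AE onset after 1st avelumab administration until up to 90 days after last dose", and it is mandatory: "All criteria listed in the left column need to be fulfilled for an event to meet the case definition of immune-mediated reaction".

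Section 17.2.3 then introduces its irAE summaries with "The following tables will be created for treatment emergent irAEs". The two irAE rows in the Section 17.1.1 overview are also for treatment-emergent events. Section 17.1 counts an event as treatment-emergent if it starts or worsens in the on-treatment period. Section 11 of the same SAP runs that period from first dose "through minimum (30 days + last dose of study treatment", the other term of the minimum being the day before a new anti-cancer drug therapy starts. For irAEs that begin later, Section 17.2.3 provides a listing.

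The protocol collects these later events. Section 7.4.1.3 extends adverse event reporting to the end of safety follow-up, "defined as 10 weeks (Part A) / 90 days (Part B) after the last study drug administration". Section 7.1.5 asks for follow-up of suspected related events, "especially for the occurrence of new autoimmune events up to 3 months after the last dose of avelumab".

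**The concern.** The SAP uses one window to decide what an irAE is and a shorter one to count irAEs. A reader who sees irAEs defined by the Appendix II case definition will naturally take the tabulated percentage as the incidence under that definition. It is the incidence of a subset.

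What is missing is an estimate, over all treated subjects, of irAE incidence, of the grade 3 or higher rate and of irAE deaths for the period that the SAP itself regards as relevant. Protocol Section 3.6 names irAEs as a primary risk of avelumab, Section 7.4.1.1 makes potential irAEs the predefined events of special interest, and Section 5.1 gives Part B a confirmatory role for some approvals. The Part B irAE figures are therefore likely to be relied on.

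**Working it through.** The plan states no figure to reproduce. The check sets the two windows side by side and then looks for any Part B table that would count a late irAE.

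**Windows after last dose**

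- Case definition (Appendix II, Table 13): up to 90 days.
- Adverse event collection, Part B (protocol 7.4.1.3): 90 days.
- Tabulation (SAP Sections 11 and 17.1): the smaller of 30 days and the time to the day before a new anti-cancer drug, so at most 30 days.
- Gap: 90 − 30 = 60 days at least, or 60/90 = 67% of the post-dose part of the case definition. It is wider if a new drug starts before day 30.

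The 67% is a share of post-dose calendar days. It is not a share of irAEs, because all on-treatment time is tabulated.

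**Where a new-onset irAE in the gap would appear**

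- 17.1.1 overview, irAE rows: not counted (treatment-emergent only).
- 17.1.2 discontinuation tables: not counted (Section 17.1 analyses are limited to treatment-emergent events unless otherwise specified).
- 17.2.1 deaths: a fatal case is counted among all deaths, with no 30-day limit on that count, but is not identified as an irAE.
- 17.2.2 SAE tables: no treatment-emergent limit is stated, so a serious case may be counted, again without the irAE label.
- 17.2.3 irAE tables: not counted.
- Listings: it appears in the 17.2.3 listing of irAEs after the on-treatment period and in the general adverse event, non-treatment-emergent and post-period listings.

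The number of irAE frequency tables that cover the gap is therefore 0. The overall irAE table in 17.2.3 has one row for all irAEs and another for irAEs, with no stated difference. Both fall under the treatment-emergent heading, so neither can be assumed to cover the later period.

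**Size**

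If k subjects have an irAE only in the gap, the overall irAE incidence differs between the two windows by k/N. With the planned N = 112, one such subject is 1/112 = 0.9 percentage points. The documents give neither k nor a rate from which to derive it. For the overall row, only subjects without an earlier tabulated irAE add to k. For a subcategory row, a late event in a new subcategory also adds.

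**The case against.** The split is prespecified and disclosed. Protocol Section 8.5.4 defines the same on-treatment period and says that adverse events starting or worsening after it are handled in separate reporting. The SAP does this with a dedicated irAE listing, and its irAE listing text gives times from first and most recent dose. Table 13 is a rule for classifying events, and a classification window may differ from a reporting window without contradiction. The Part B secondary safety endpoint is the occurrence and severity of treatment-related events, not an irAE rate. Safety is analysed descriptively, and no decision rule depends on this count.

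All of that stands, and it makes this a gap in estimation rather than an error against the protocol. It does not close the gap. Separate reporting does not mean listing only: a separate column or table would also comply. A listing gives no percentage, grade 3 or higher rate or subcategory count.

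Two stronger readings do not hold. A reader might infer that delayed irAEs go unreported or enter no incidence table of any kind. They are listed, and serious or fatal ones may be counted in Sections 17.2.1 and 17.2.2. A reader might also infer that the loss falls mainly on subjects who stopped for toxicity. An irAE that starts during treatment and causes discontinuation is tabulated, as is one that worsens within the window. What is missed is new onset after the window, which by construction arises after dosing has ended.

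**Conclusion.** The point holds in limited form. Part B adopts a 90-day irAE definition and plans no irAE frequency table beyond 30 days after last dose, or beyond the start of a new anti-cancer drug if that comes first. The case-definition incidence, the grade 3 or higher rate and irAE deaths over that window are therefore not estimated.

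It would be tempting to turn this into a number of missed subjects or percentage points. That needs an assumed proportion off treatment by the cut-off and an assumed late irAE rate, and the documents supply neither. The supportable statement is 0.9 percentage points per subject, assuming 112 treated subjects. No efficacy result is affected. This is an inexpensive improvement worth making, because a safety figure that readers will rely on does not match its own stated definition.

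**What to change.** Keep the treatment-emergent irAE tables as planned. In Sections 17.1.1 and 17.2.3, add a second column or table for irAEs with onset from first dose to 90 days after last dose, covering all irAEs, grade 3 or higher, those leading to death, and counts by subcategory. Flag events that arise after a new anti-cancer drug, or show them separately. In the same edit, state how the two similarly named rows of the overall irAE table differ, or delete one.

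No new data are needed. Collection already runs to 90 days, the Appendix II review already applies that window, and the planned listing already requires the late events to be identified. The work is a second window in existing table programs.

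The downside is a somewhat higher reported irAE rate and less certain attribution once another drug has started. Table 13's etiology criterion, which requires that no other cause is clear or that pathology supports an immune mechanism, already screens such events in part, and the flag lets a reader set the rest aside. The 90-day column should be labelled so that it is not read against the 30-day rows beside it, or against Part A, where the irAE tables are also treatment-emergent and collection ends at 10 weeks.
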